4.1.1.2.4. Early Discontinuation of Treatment Visit

Participants unable or unwilling to continue the study treatment for any reason will perform an early discontinuation of treatment (ED) visit. If the participant is discontinuing during an unscheduled visit, that visit should be performed as the ED visit. If the participant is discontinuing during a scheduled visit, that visit should be performed as an ED visit. Procedures should be completed according to the Schedule of Activities (Section 1.3). Patient-reported outcomes questionnaires should be administered as early as possible, as per Suggested Visit Structure (Section 10.8). Administration of mental health questionnaires should follow assessment for AEs (see Section 7.2).

4.1.1.2.5. Safety Follow-up Period

Visit 801 or Visit 802

All participants are required to complete a safety follow-up visit (Visit 801 or Visit 802), according to the Schedule of Activities (Section 1.3). Participants discontinuing the study early and performing an ED visit will also be asked to perform the safety follow-up visit. During the safety follow-up period, participants will not receive study drug. Participants are also required to return any remaining study diaries to the study site at the end of this period.

For participants who discontinue or complete the study within the first 72 weeks, Visit 801 (safety follow-up visit) should be performed 4 weeks after the last treatment visit (Visit 21 or 99) or 4 weeks after the ED visit for those who decline to return for Visit 99. Participants with prediabetes continuing to Week 78 should not perform Visit 801.

For those participants without glycemic evidence of T2DM (Section 4.1.2.1), a 2-hour oral OGTT will be performed at Visit 802.

4.1.2. Study Procedures

Participants will perform study procedures listed in the Schedule of Activities (Section 1.3).

Participants will be permitted to use concomitant medications that they require during the study, except certain medications that may interfere with the assessment of efficacy and safety characteristics of the study treatments (Section 5.2).

Study governance considerations are described in detail in Section 10.1 (Appendix 1).

4.1.2.1. Definition of Prediabetes

The duration of treatment in Study GPHK (SURMOUNT-1) is determined by glycemic status at randomization, categorized into those with prediabetes or normoglycemia (participants with T2DM are excluded), as defined by the 2019 American Diabetes Association Standards of Medical Care in Diabetes (American Diabetes Association 2019b). The following populations are defined:

	Normoglycemia	Prediabetes	Diabetes
Fasting glucose Obtained alone or at time = 0 during an OGTT	<100 mg/dL (<5.6 mmol/L)	100-125 mg/dL (5.6-6.9 mmol/L)	≥126 mg/dL (≥7.0 mmol/L)
2H glucose Obtained at time = 120 min during an OGTT	<140 mg/dL (<7.8 mmol/L)	140-mg-199 mg/dL (7.8-11.0 mmol/L)	≥200 mg/dL (≥11.1 mmol/L)
HbA1c	<5.7% (<39 mmol/mol)	5.7%-6.4% (39-47 mmol/mol)	≥6.5% (≥48 mmol/mol)

Abbreviations: H = hour; HbA1c = hemoglobin A1c; OGTT = 2-hour oral glucose tolerance test.

Screening to determine randomization glycemic status will occur in 2 visits:

Screening Visit 1

Participants will have a fasting glucose (FG) and HbA1c test. Results of these tests determine eligibility to proceed to Screening Visit 2.

- FG ≥126 mg/dL (7.0 mmol/L) OR HbA1c ≥6.5% (48 mmol/mol) suggests DM. These participants are **excluded** from the study and should be referred to their primary care physician for further work-up to confirm the diagnosis.

- All participants otherwise eligible and without FG or HbA1c values suggestive of diabetes will proceed to Screening Visit 2

Screening Visit 2

All participants attending Screening Visit 2 will undergo a 2-hour OGTT test. These results, in combination with those obtained from Screening Visit 1, will be used to determine study eligibility and randomization glycemic status.

- 2-hour OGTT results: FG ≥ 126 mg/dL (≥ 7.0 mmol/L) OR 2-hour OGTT ≥ 200 mg/dL (≥ 11.1 mmol/L) suggests diabetes mellitus. These participants are ***excluded*** from the study and should be referred to their primary care physician for further work-up to confirm the diagnosis.

Glycemic Classification

All participants without laboratory tests suggestive of diabetes will be classified as having either normoglycemia or prediabetes. In keeping with American Diabetes Association guidelines (American Diabetes Association 2019b), at least 2 abnormal tests are required to diagnose prediabetes. For example:

- Both 0 AND 2-hour values during the 2-hour OGTT values are in the prediabetes range.
- FG at Screening Visit 1 AND Visit 2 are in the prediabetes range.
- FG at Screening Visit 1 AND 2-hour values during 2-hour OGTT are in the prediabetes range.
- HbA1c AND 1 of either the FG or 2-hour OGTT values are in the prediabetes range.

4.1.2.2. Oral Glucose Tolerance Test

Participants should attend visits requiring a 2-hour OGTT in the fasting state. Samples will be collected at 0, 30, 60, 90, and 120 minutes during the 2-hour OGTT, unless the OGTT is repeated to confirm the diagnosis of diabetes. For glycemic classification, the values at time = 0 min (FG) and 120 minutes (2-hour OGTT) will be used. If a 2-hour OGTT is repeated to confirm the diagnosis of diabetes (see Section 4.1.2.3), only samples at 0 and 120 minutes for glucose measurement will be collected.

Two-hour OGTTs should be performed per the Schedule of Activities (Section 1.3) and as described in Section 10.7, until such time as a protocol-defined diagnosis of diabetes is confirmed (see Section 4.1.2.3). Two-hour OGTT testing should be omitted at visits following a protocol-defined diabetes diagnosis.

4.1.2.3. Definition and Management of Incident Diabetes

Definition of incident diabetes

Incident diabetes is defined when any 1 of the following occur after randomization (American Diabetes Association 2019b):

- unequivocal hyperglycemia (random glucose ≥ 200 mg/dL) with signs or symptoms of hyperglycemia

- any 2 of the following criteria are observed at the same visit, or 1 abnormal value is observed and subsequently confirmed:
 - HbA1c $\geq 6.5\%$ (48 mmol/mol)
 - FG or 0-hour serum glucose from 2-hour OGTT ≥ 126 mg/dL (7.0 mmol/L)
 - 2-hour glucose ≥ 200 mg/dL (11.1 mmol/L) by a 2-hour OGTT
- initiation of any medication for the treatment of diabetes

Confirmation of diabetes diagnosis

In the event 1 abnormal value is observed (HbA1c $\geq 6.5\%$ [48 mmol/mol]) OR fasting glucose (or 0-hour serum glucose from 2-hour OGTT) ≥ 126 mg/dL (7.0 mmol/L) OR 2-hour glucose from 2-hour OGTT ≥ 200 mg/dL (11.1 mmol/L)* after randomization, the abnormal test should be repeated within 4 weeks to confirm diagnosis of diabetes and to ensure that diabetes management is initiated without delay.

*If the abnormal value observed is 2-hour glucose from the OGTT ≥ 200 mg/dL (11.1 mmol/L), the 2-hour OGTT should be repeated within 4 weeks (only samples at 0 and 120 minutes for glucose measurement will be collected).

The diagnosis of diabetes is confirmed if any of the following occur:

- HbA1c $\geq 6.5\%$ (48 mmol/mol) is observed at 2 measurements any time during the study.
- 2-hour glucose ≥ 200 mg/dL (11.1 mmol/L) during an OGTT is observed at 2 measurements any time during the study.
- FG value ≥ 126 mg/dL (7.0 mmol/L) is observed at a consecutive FG measurement (either at a scheduled or an unscheduled visit) following an isolated FG (or 0-hour serum glucose from 2-hour OGTT) value ≥ 126 mg/dL (7.0 mmol/L).
 - If diabetes diagnosis has not been confirmed at the consecutive FG measurement, another FG (or 0-hour serum glucose result from 2-hour OGTT) result ≥ 126 mg/dL (7.0 mmol/L) observed during the study will be considered as a new finding requiring confirmation.

Note: Once diabetes has been confirmed, repeating any future abnormal test within 4 weeks is no longer required.

Recording of incident diabetes events

- Diabetes diagnosis and the onset date as assessed by investigator will be recorded in the AE eCRF and the dedicated endpoint eCRF.
- If the diagnosis of diabetes is based on laboratory results, the date of the first abnormal HbA1c or glucose value within the diabetes range should be indicated as the date of diagnosis, unless, in the investigator's opinion, a different date is more appropriate. If the diagnosis is based on initiation of any medication for the treatment of diabetes, the investigator should indicate the most probable date of diagnosis in the eCRFs.

- All reported or suspected cases of incident diabetes will be adjudicated by an independent clinical endpoint committee (adjudication committee).
- Decisions of the adjudication committee regarding diabetes diagnosis and the onset date will be recorded in the dedicated adjudication eCRF.

Management of incident diabetes

Participants who develop diabetes during the study will be

- provided and trained to use a glucometer
- educated on the signs and symptoms of hypoglycemia and its treatment, and
- provided a diary to record hypoglycemic episodes per Section 10.3.1.1.

Participants will be referred to their usual care provider and provided with a letter showing the study results indicative of diabetes. The decision to further evaluate, to initiate antihyperglycemic therapy, and the choice of antihyperglycemic medication will be at the discretion of the participant's usual care provider, with the exception of use of dipeptidyl-peptidase-4 (DPP-4) inhibitors and open-label GLP-1R agonists, which are prohibited in the study. Monitoring for hypoglycemia includes capture of events as defined in Section 10.3 (Appendix 3).

4.2. Scientific Rationale for Study Design

Tirzepatide is a 39-amino acid synthetic peptide with agonist activity at both the GIPR and GLP-1R. Its structure is based on the GIP sequence and includes a C20 fatty di-acid moiety (Coskun et al. 2018). It is administered QW by SC injection.

As a dual GIP/GLP-1R agonist, tirzepatide could exceed the efficacy of selective GLP-1R agonists by recruiting metabolically active tissues not targeted by selective GLP-1R agonists (for example, adipose tissue as indicated by the observation of increased energy utilization) (Baggio and Drucker 2007) and has the potential to reach higher efficacy in target tissues, such as insulin-producing pancreatic beta cells that express both GIPR and GLP-1R, before reaching its therapeutic limitation. Results from a Phase 2 study (GPGGB) demonstrated that tirzepatide use in participants with T2DM was associated with a substantial, dose-dependent weight loss, greater than the weight change observed with dulaglutide, a specific GLP-1R agonist. General safety characteristics of all studied doses of tirzepatide were similar to that of the GLP-1R agonist class, consisting mainly of nausea, vomiting, and diarrhea. In general, these events were transient and mild or moderate in severity, with few severe episodes. Although GI AEs were more common at the 15-mg arm of tirzepatide, this dose demonstrated the highest efficacy in terms of weight loss.

This suggests that tirzepatide has the potential to become a medication for chronic weight management. An optimized dose escalation regimen, proposed in the Study GPHK (SURMOUNT-1) to improve tolerability (and supported by a dose-escalation algorithm from study GPGF), should enable a use of higher doses to maximize effects on body weight. Study GPHK (SURMOUNT-1) is designed to determine the comparative benefits and risks of

tirzepatide 5 mg, 10 mg or 15 mg QW versus placebo in participants who have obesity or are overweight. A double-blind design was selected to minimize participant and investigator bias in assessments for efficacy, safety, and study drug tolerability.

A placebo comparator was selected for this trial in accordance with regulatory guidance (FDA 2007; EMA 2016). In addition, all participants, regardless of treatment assignment, will receive lifestyle modification counselling consistent with current guidelines for weight management (Jensen et al. 2013). Specifically, participants will consult with a dietician, or equivalent qualified delegate, throughout the study to achieve at least a 500 kcal/day energy deficit through a combination of caloric restriction and increased physical activity (Section 5.3.1). The planned duration of treatment for the primary endpoint at 72 weeks allows for at least a 52-week treatment period at the dose achieved following dose escalation to either 5, 10, or 15 mg. This duration is considered appropriate to assess the full effects and benefit/risk of each maintenance dose of tirzepatide compared with placebo on body weight and is consistent with regulatory guidelines (FDA 2007; EMA 2016).

The effects of drug cessation will be assessed in the 4-week and in the 12-week safety follow-up/observational periods

Another objective of the study is to evaluate the effect of tirzepatide on the risk of new-onset diabetes. Obesity is associated with an increased risk of developing T2DM and diabetes prevention is of a great importance in obese subjects to protect them from complications of the disease. Several studies have shown that interventions leading to weight loss may help prevent diabetes (Adams et al. 2017, le Roux et al. 2017).

To obtain additional information regarding the rate of conversion to diabetes on tirzepatide, participants with prediabetes diagnosed at the beginning of the study (being at increased risk of diabetes), will be treated and observed for an additional 2 years. Based on available literature, the 3 years of treatment with tirzepatide should be sufficient to demonstrate the risk reduction of developing T2DM compared to placebo. This additional treatment period would also permit collecting data on the durability of weight changes with long-term therapy and safety of long-term tirzepatide treatment.

To minimize the potential confounding effect of changes to concomitant medications, participants will be permitted to use concomitant medications that do not interfere with the assessment of efficacy or safety characteristics of the study treatments.

4.3. Justification for Dose

Tirzepatide doses of 5 mg, 10 mg, and 15 mg QW will be evaluated in this study. These doses and associated escalation schemes were selected based on assessment of safety, efficacy (weight loss), and GI tolerability data, followed by exposure-response modeling of data in patients in Phase 1 and 2 studies that predicted weight loss in obese and overweight patients without T2DM.

Dosing algorithms starting at a low dose of 2.5 mg accompanied by dose escalation of 2.5-mg increments every 4 weeks should permit time for development of tolerance to GI events and are predicted to minimize GI tolerability concerns. The maximum proposed dose of 15 mg maintains an exposure multiple of 1.6 to 2.4 to the no-observed adverse-effect level doses in 6-month monkey and rat toxicology studies.

4.4. End of Study Definition

Section 7.2 describes the criteria used to determine if a participant has completed the study.

The end of the study is defined as the date of the last visit of the last participant in the study or the last scheduled procedure shown in the Schedule of Activities (Section 1.3.1 or 1.3.2 based on randomization glycemic status), for the last participant in the trial globally.

5. Study Population

Prospective approval of protocol deviations to recruitment and enrollment criteria, also known as protocol waivers or exemptions, is not permitted.

5.1. Inclusion Criteria

Participants are eligible to be included in the study only if all of the following criteria apply:

Type of Participant and Disease Characteristics

1. Have a BMI
 - ≥ 30 kg/m² or
 - ≥ 27 kg/m² and previously diagnosed with at least one of the following weight related comorbidities:
 - hypertension: treated or with systolic blood pressure (SBP) ≥ 130 mmHg or diastolic blood pressure ≥ 80 mmHg
 - dyslipidemia: treated or with low-density lipoprotein (LDL) ≥ 160 mg/dL (4.1 mmol/L) or triglycerides ≥ 150 mg/dL (1.7 mmol/L), or high-density lipoprotein (HDL) < 40 mg/dL (1.0 mmol/L) for men or HDL < 50 mg/dL (1.3 mmol/L) for women
 - obstructive sleep apnea
 - cardiovascular disease (for example, ischemic cardiovascular disease, New York Heart Association (NYHA) Functional Class I-III heart failure)
2. Have a history of at least one self-reported unsuccessful dietary effort to lose body weight
3. In the investigator's opinion, are well-motivated, capable, and willing to
 - learn how to self-inject study drug, as required for this protocol (visually impaired persons who are not able to perform the injections must have the assistance of a sighted individual trained to inject study drug; persons with physical limitations who are not able to perform the injections must have the assistance of an individual trained to inject study drug)
 - inject study drug (or receive an injection from a trained individual if visually impaired or with physical limitations)
 - follow study procedures for the duration of the study, including, but not limited to: follow lifestyle advice (for example, dietary restrictions and exercise plan), maintain a study diary, and complete required questionnaires

Participant Characteristics

4. Are 18 years or older

a. male participants:

- Male participants with partners of childbearing potential should be willing to use reliable contraceptive methods throughout the study and for 5 half-lives of study drug plus 90 days, corresponding to 4 months after the last injection.

b. female participants:

- Female participants not of childbearing potential may participate and include those who are:
 - infertile due to surgical sterilization (hysterectomy, bilateral oophorectomy or tubal ligation), congenital anomaly such as Mullerian agenesis
 - postmenopausal, defined as either
 - a woman at least 40 years of age with an intact uterus, not on hormone therapy, who has cessation of menses for at least 1 year without an alternative medical cause, AND a follicle-stimulating hormone ≥ 40 mIU/mL; women in this category must test negative in pregnancy test prior to study entry
 - or**
 - a woman 55 or older not on hormone therapy, who has had at least 12 months of spontaneous amenorrhea
 - or**
 - a woman at least 55 years of age with a diagnosis of menopause prior to starting hormone replacement therapy
- Female participants of child-bearing potential (not surgically sterilized and between menarche and 1-year postmenopausal) must:
 - test negative for pregnancy at Visit 1 based on a serum pregnancy test
 - and**
 - if sexually active, agree to use 2 forms of effective contraception, where at least 1 form is highly effective, for the duration of the trial and for 30 days thereafter
 - not be breastfeeding

Informed Consent

5. Have given written informed consent to participate in this study in accordance with local regulations and the ethical review board (ERB) governing the study site

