Vital signs (3 sitting BP and HR)	Vital-sign measurements should be taken before obtaining an ECG tracing and before collection of blood samples for laboratory testing, per the instruction in Section 10.7.
Hand out diary, instruct in use	All training should be repeated as needed to ensure participant compliance.
Review study participant diary and study-drug compliance	Data from diary, as well as study drug compliance, should be reviewed.

Lifestyle Program instructions	Counselling on diet and exercise, to be performed by a dietician or equivalent qualified delegate, to include calculation of individualized energy requirement and methods to change dietary composition and amount of physical activity. The Lifestyle Program Instruction may be delivered on a separate day from the rest of that visit’s study procedures but must occur within the visit window. Beginning at Week 8, the Lifestyle Program Instruction may be delivered by phone.
Review diet and exercise goals	All training should be repeated as needed to ensure participant compliance. Study personnel to provide reinforcement and encouragement for lifestyle modifications.
Injection training with Autoinjector demonstration device	All training should be repeated as needed to ensure participant compliance
Dispense study drug Visit 72	This applies only to those participants going into the additional 2-year treatment period for participants with prediabetes at randomization.
Observe participant administer study drug	Participants should administer their first dose of study drug at the end of the Visit 3, after other study procedures are completed
Serum pregnancy test	A serum pregnancy test will be performed at Visit 1 for women of childbearing potential only.
Urine pregnancy test	A urine pregnancy test must be performed at Visit 3 with the result available prior to randomization and first injection of study drug(s) for women of childbearing potential only. Additional pregnancy tests (beyond those required per the Schedule of Activities) should be performed at any time during the trial if a menstrual period is missed, there is clinical suspicion of pregnancy, or as required by local law or regulation.
Follicle-stimulating hormone test	Follicle-stimulating hormone test performed at Visit 1 for postmenopausal women at least 40 years of age with an intact uterus, not on hormone therapy, and who have had spontaneous amenorrhea for more than 1 year without an alternative medical cause.

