10.2. Appendix 2: Clinical Laboratory Tests

- The tests detailed below will be performed by the central laboratory unless otherwise stated.
- Local laboratory results are only required in the event that the central laboratory results are not available in time for response evaluation. If a local sample is required, it is important that the sample for central analysis is obtained at the same time. Additionally, if the local laboratory results are used to make either a study intervention decision or response evaluation, the results must be entered into the eCRF.
- Protocol-specific requirements for inclusion or exclusion of participants are detailed in Section 5 of the protocol.
- Additional tests may be performed at any time during the study as determined necessary by the investigator or required by local regulations.
- Refer to Section 5.1 (Inclusion Criteria) for screening pregnancy criteria.

Investigators must document their review of each laboratory safety report.

Laboratory/analyte results that could unblind the study will not be reported to investigative sites or other blinded personnel until the study has been unblinded.

Clinical Laboratory Tests**Hematology^a**

Hemoglobin
Hematocrit
Erythrocyte count (RBC)

Mean cell volume
Mean cell hemoglobin concentration
Leukocytes (WBC)
Neutrophils, segmented
Lymphocytes
Monocytes
Eosinophils
Basophils
Platelets

Urine Chemistries^a

Albumin
Creatinine

Nonpharmacogenetic Stored Samples

Serum
EDTA plasma
P800 plasma

Pharmacokinetics samples^{a,e,f,g}**Pharmacogenetics Sample**

Whole blood (EDTA)

Oral Glucose Tolerance Test (glucose, insulin^c,
c-peptide^c)

Cystatin-C^a

HbA1c^a

Endocrine^a

Calcitonin
Thyroid-stimulating hormone (TSH)

Insulin^c

C-peptide^c

Clinical Chemistry^a

Sodium
Potassium
Bicarbonate
Total bilirubin
Direct bilirubin
Alkaline phosphatase
Alanine aminotransferase (ALT)
Aspartate aminotransferase (AST)
Blood urea nitrogen (BUN)
Creatinine
Uric acid
Calcium
Glucose, fasting
Albumin
Total Cholesterol
Triglycerides
Creatine kinase (CK)

Hormones (females)

Pregnancy Test ^a, serum and/or urine^b
Follicle-stimulating hormone (FSH)^d

Calculations

eGFR (calculated by CKD-EPI equation)^{a,c}
UACR (urine albumin mg/dL/creatinine g/dL=UACR
mg/g)

Pancreas (exocrine) ^a

Pancreatic amylase
Lipase

Immunogenicity^{a,e,g}

Anti-tirzepatide antibodies
Anti-tirzepatide antibody neutralization

Lipid Panel^a

LDL-C
HDL-C
VLDL-C

Free Fatty Acids^c

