10.4. Appendix 4: Contraceptive Guidance and Collection of Pregnancy Information

Definitions:

Woman of Childbearing Potential

A woman is considered fertile following menarche and until becoming postmenopausal unless permanently sterile (see below).

If fertility is unclear (for example; amenorrhea in adolescents or athletes) and a menstrual cycle cannot be confirmed before first dose of study intervention, additional evaluation should be considered.

Women in the following categories are not considered women of childbearing potential

Article I. Premenarchal

Article II. Premenopausal female with 1 of the following:

- Documented hysterectomy
- Documented bilateral salpingectomy
- Documented bilateral oophorectomy

For individuals with permanent infertility due to an alternate medical cause other than the above, (for example; Mullerian agenesis, androgen insensitivity), investigator discretion should be applied to determining study entry.

Note: Documentation can come from the site personnel's review of the participant's medical records, medical examination, or medical history interview.

Article III. Postmenopausal female

- A postmenopausal state is defined as either
 - A woman at least 40 years of age with an intact uterus, not on hormone therapy, who has cessation of menses for at least 1 year without an alternative medical cause, AND a follicle-stimulating hormone (FSH) ≥ 40 mIU/mL; or
 - A woman 55 or older not on hormone therapy, who has had at least 12 months of spontaneous amenorrhea; or
 - A woman at least 55 years of age with a diagnosis of menopause prior to starting hormone replacement therapy.
- Females on HRT and whose menopausal status is in doubt will be required to use one of the nonestrogen hormonal highly effective contraception methods if they wish to continue their HRT during the study. Otherwise, they must discontinue HRT to allow confirmation of postmenopausal status before study enrollment.

Contraception Guidance:

Contraceptive use by men and women should be consistent with local regulations regarding the methods of contraception for those participating in clinical studies.

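### Section 5.1 and Appendix 4 classify a premenopausal woman with tubal ligation only in opposite ways, and no text says which definition governs her urine pregnancy tests after screening

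*Protocol*

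**What the plan says.** **Section 5.1, criterion 4b.** Women not of childbearing potential include those "infertile due to surgical sterilization (hysterectomy, bilateral oophorectomy or tubal ligation), congenital anomaly such as Mullerian agenesis". The contrasting group is introduced by "Female participants of child-bearing potential (not surgically sterilized and between menarche and 1-year postmenopausal) must". Women in that group need a negative serum test at Visit 1 and must, "if sexually active, agree to use 2 forms of effective contraception, where at least 1 form is highly effective", through the trial and for 30 days after it.

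**Section 10.4, Appendix 4.** The default is fertility until menopause, with permanent sterility as the exception. Under the line "Women in the following categories are not considered women of childbearing potential", the premenopausal entries are documented hysterectomy, "Documented bilateral salpingectomy" and documented bilateral oophorectomy. Tubal ligation is absent, both there and from the appendix's list of highly effective contraceptive methods. The appendix sets its own two-method rule.

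**Where the term is used.** The urine pregnancy test note to the Schedule of Activities (Section 1.3) requires a Visit 3 result before "randomization and first injection of study drug(s) for women of childbearing potential only". A footnote in Appendix 2 repeats this. Neither defines the term or points to a list. Appendix 2 also tells sites: "Refer to Section 5.1 (Inclusion Criteria) for screening pregnancy criteria".

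**The concern.** The protocol has two definitions of childbearing potential, and they disagree about a recognisable group of women. Two sites could each follow the protocol in good faith and handle the same woman differently. One would run no scheduled urine tests and impose no contraception duty. The other would test about every three months and ask for two methods if she is sexually active.

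What is at stake is how consistently exposure in pregnancy is detected over as much as 176 weeks of treatment. Pregnancy is a listed reason for stopping study drug (Section 7.1), and a participant who becomes pregnant is withdrawn (Section 7.2 and Appendix 4). The sponsor has already edited this pair of sections for consistency: the amendment history (Section 10.12) records removal of an Appendix 4 note because it might cause inclusion criterion 4 to be misread.

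**Working it through.** **Step 1: classify the woman under each list.** Take a premenopausal woman whose only procedure is tubal ligation.

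| Procedure | Exempt under 5.1 | Exempt under Appendix 4 |
|---|---|---|
| Hysterectomy | yes | yes, if documented |
| Bilateral oophorectomy | yes | yes, if documented |
| Tubal ligation | yes | not listed |
| Bilateral salpingectomy | not named | yes, if documented |

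The lists conflict on tubal ligation. They also differ the other way on bilateral salpingectomy, although 5.1's general reference to surgical sterilization could cover it.

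**Step 2: look for text that settles it.**

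- Appendix 2 points to 5.1 for screening. That settles the Visit 1 serum test and goes no further.
- Section 8.3.4 points to Appendix 4 only for what to do once a pregnancy is reported.
- Appendix 4's investigator-discretion clause concerns permanent infertility from another medical cause (its examples are Mullerian agenesis and androgen insensitivity) and concerns study entry. It does not clearly reach tubal ligation, and it does not reach on-study testing.
- Section 5.1 applies its contraception rule to the whole trial under its own definition. Appendix 4 states a contraception rule under a different definition. Neither defers to the other.

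No precedence statement was found for the urine tests after screening.

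**Step 3: count the scheduled urine tests (Sections 1.3.1 and 1.3.2).** Early discontinuation visits are excluded, and Visit 99 is taken as replacing Visit 21.

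- To Week 72: Visits 3, 6, 9, 12, 15, 18 and 21, at Weeks 0, 12, 24, 36, 48, 60 and 72. That is 7 tests. Visit 3 precedes the first dose, so 7 − 1 = 6 come after it.
- Extension for participants with prediabetes: Visits 102, 104, 106, 108, 110, 112, 114 and 116, at Weeks 85, 98, 111, 124, 137, 150, 163 and 176. That is 8 tests.
- Total to Week 176: 7 + 8 = 15, of which 15 − 1 = 14 come after the first dose.
- Spacing: 12 weeks to Week 72, then 13 weeks.

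Under 5.1 the count is 0. Under Appendix 4 it is 7 for a woman treated to Week 72 and 15 for one treated to Week 176. An early discontinuation visit held as an unscheduled visit would add 1.

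**Step 4: state the inference.** The restriction to women of childbearing potential is attached in the note to the Visit 3 urine test. The note gives no separate scope for later scheduled tests. Applying the same limit to them is the natural reading, but it is a reading, and the comparison of 0 with 15 depends on it.

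**Step 5: number of women.** The cap on women gives at most 0.70 × 2400 = 1680. The documents say nothing about how many would be premenopausal with tubal ligation only, so no count is offered.

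**The case against.** The strongest reply is that 5.1 already governs. Its contraception duty runs through the trial and beyond, on a definition given in the same bullet. Status is set at entry, and nothing tells a site to reclassify a woman later from Appendix 4. Carrying the 5.1 status forward is therefore a sensible default. For contraception this largely stands: a reader might infer that no rule covers her on study, but 5.1 supplies one and Appendix 4 contradicts it. For the urine tests it stands only in part, because the pointer to 5.1 is confined to screening and Appendix 4 offers a competing definition without qualification.

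The second reply is that little follows in practice. The Schedule of Activities note calls for extra tests at any time for a missed period, clinical suspicion or local requirement, and this is not tied to either list. A missed period would usually prompt a test before the next 12- or 13-week visit. This stands. A reader might infer from a count of 0 that pregnancy on study drug would go undetected. The documents do not support that, and they give no pregnancy risk after tubal ligation from which to estimate harm.

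**Conclusion.** The contradiction is real and can be read directly from the two lists. Its size is 0 against up to 15 scheduled urine tests per affected woman (7 if she stops at Week 72). This assumes that the childbearing-potential limit covers all scheduled urine tests and leaves early discontinuation visits aside. On contraception, the contrast is no duty under 5.1 against two methods under Appendix 4, which accepts habitual abstinence.

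The Visit 1 serum test is not in doubt. The number of women affected is unknown, the unscheduled tests limit the safety effect, and no endpoint, sample size or error rate is touched. This is a minor inconsistency between two safety rules, worth correcting because the correction is cheap.

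**What to change.** Use one identical list in Sections 5.1 and 10.4. Have the pregnancy-test note in the Schedule of Activities refer to that list and say that it applies to all scheduled urine tests.

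**Preferred, because it keeps on-study testing:**

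1. In criterion 4b, replace the parenthetical with documented hysterectomy, bilateral salpingectomy or bilateral oophorectomy.
2. In 10.4, state that a woman whose only procedure is tubal ligation is pregnancy tested per Section 1.3.
3. In both 5.1 and 10.4, state how tubal ligation counts toward the two-method rule. It is not now among the highly effective methods, so the sponsor has to decide this. Any exemption from a second method for women already enrolled must be written into both sections, or a new inconsistency replaces the old one.

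**If the sponsor intends tubal ligation to exempt:** add it to the 10.4 list and add bilateral salpingectomy to 5.1, so that the lists match in both directions.

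**Cost:** wording in three places and a site memo. Under the preferred edit, each affected woman has up to 15 urine tests, plus the Visit 1 serum test if she is still to be screened. Depending on item 3, a sexually active woman may also need an added contraceptive method. No endpoint or analysis changes.
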